6.2 ACCESS TO BLINDED TREATMENT ASSIGNMENT

This study is an open-label study.

6.3 COMPLIANCE

It is anticipated that subjects will follow dosing and titration regimens consistent with the study drug dosing instructions of the study. Routine contact between study site personnel and the subject should be conducted to monitor AEs between scheduled study visits. Study site personnel will record study drug dose at every study visit in the source documentation.

The Investigator, other study site personnel, or nursing support under the direction of the Investigator, will be responsible for dose titration of study drug. During telephone calls, study site personnel and/or nursing support, with oversight of the Investigator, will evaluate and

adjust the current dose of study drug and assess whether the subject is taking the study drug as prescribed.

Arrangements will be made to ensure the subject has adequate drug supply with respect to their study visit schedule. Additional Remodulin and/or Orenitram supply may occur between protocol study visits if needed. Subjects should be instructed to return all used and unused Remodulin and Orenitram, including empty vials/bottles, to the appropriate study personnel on an ongoing basis at every study visit.

Upon return of study drug, study personnel or a pharmacist must document the number of returned tablets of each strength or vials of each strength on the subject's study drug accountability log. Used and unused vials and bottles of study drug should be retained by the study site or pharmacy and returned to a Sponsor-designated location for destruction, or destroyed and documented according to institutional policy following consultation with the Sponsor after final drug accountability by Sponsor personnel.

Every subject will be asked at the study visits whether he/she has been adherent with dosing instructions. If a subject is not adherent, then study site personnel must re-educate the subject on proper dosing and its importance. Continued nonadherence could lead to withdrawal of the subject from the study based on discussions between the Investigator and Sponsor.

7 EXPERIMENTAL PROCEDURES

The following study visits will occur during the 16-week study at the following time points: Screening, Baseline, Week 2 (Day 15 [±3 days]), Week 4 (Day 29 [±5 days]), Week 8 (Day 57 [±5 days]), Post Transition Visit (7 to 14 days after Transition Visit), Week 12 (Day 85 [±5 days]), and Week 16/Early Study Withdrawal (Day 113 [±7 days]). The Transition Visit should occur at Weeks 2, 4, or 8.

Written informed consent must be obtained from all subjects (signed and dated by subject) prior to study procedures. The patient-reported outcomes (ie, TSQM and the emPHasis-10 questionnaire) should be completed by the subjects prior to other assessments listed in Table 3-1. Subject information from assessments listed in Table 3-1, including the

patient-reported outcomes, will be collected and recorded into an EDC system by study site personnel or the Investigator.

7.1 SCREENING (DAYS -28 TO -1)

At Screening, after an Investigator reviews the subject's ICF and obtains the subject's signed and dated written ICF, the Investigator will review and verify the subject's inclusion criteria and exclusion criteria, and assign every eligible subject a unique subject identification. If a subject withdraws from participation in the study, then his/her subject identification cannot be reused. Subjects who fail to meet the eligibility criteria should not, under any circumstances, be enrolled.

All subjects will be assessed for eligibility during the 28-day Screening window. The following Investigator-reported assessments will be conducted after the subject signs the ICF:

- WHO FC assessment
- Serum NT-proBNP (sample must be drawn prior to the 6MWT initiation)
- 6MWT (after 10 minutes rest [seated]), immediately followed by heart rate recovery (1 minute) and Borg dyspnea score
- Clinical laboratory assessments
- Vital signs (prior to or at least 30 minutes after the 6MWT, and after 5 minutes of rest seated)
- Full physical examination
- Concomitant medications
- CD4 count for subjects with HIV infection
- Female subjects of childbearing potential will undergo a urine pregnancy test.
- Subject AEs will be recorded continuously from when the subject signs the ICF until the subject completes the study or is withdrawn from the study.
- The subject's medical history, PAH history, prior PAH medications, and demographics will be recorded.
- Cardiac index measured by Swan-Ganz RHC will be assessed during Screening if the subject has not had an RHC within 180 days of Baseline with a cardiac index ≥2.0 L/min/m² with no changes in PAH medication regimen since the RHC

7.1.1 Re-screening of Subjects

Subjects with short-term musculoskeletal conditions (eg, sprained ankle) can be re-screened. The Baseline 6MWT must be conducted free of any unusual or extenuating circumstances (eg, intercurrent illness other than that under study, ankle or knee sprains, unusual pain affecting the lower limbs, respiratory infection, etc). If there is any unusual or extenuating circumstance at Baseline, the visit should be postponed so that there is adequate time for the recovery of the subject. If the 28-day Screening window is exceeded by the subject's recovery, the subject can be re-screened at a later time when the unusual or extenuating circumstance is adequately resolved, so as to not impact the results of the Baseline 6MWT.

7.2 BASELINE (DAYS -14 TO -1)

The following subject-reported data will be completed by the subject at Baseline prior to all other assessments: emPHasis-10 questionnaire and TSQM.

Baseline assessments can be conducted up to 14 days prior to starting the Remodulin infusion. The following Investigator-reported assessments will be conducted:

- Inclusion and exclusion criteria assessment
- ECHO
- WHO FC assessment
- Serum NT-proBNP (sample must be drawn prior to the 6MWT and Remodulin initiation)
- 6MWT (after 10 minutes rest [seated]), immediately followed by heart rate recovery (1 minute) and Borg dyspnea score
- Clinical laboratory assessments
- Vital signs (prior to or at least 30 minutes after the 6MWT, and after 5 minutes of rest seated)
- Concomitant medications
- Optional pharmacogenomic (genetic/RNA) and biomarker blood samples
- Female subjects of childbearing potential will undergo a urine pregnancy test
- Subject AEs will be recorded
- AE Bothersome Survey
- The subject's medical history, PAH symptom score, and prior PAH medications will be recorded.

7.3 TREATMENT PHASE

Following completion of Baseline assessments, Remodulin will be initiated at 2 ng/kg/min SC or IV in an inpatient or outpatient setting. Intravenous Remodulin may be administered through an indwelling central venous catheter or a peripherally inserted catheter as clinically indicated. For subjects receiving IV Remodulin through a central venous catheter, it is recommended that the central venous catheter be retained for at least 28 days after the transition from Remodulin.

Up-titration of Remodulin will continue as tolerated. Subjects should be optimized on Remodulin therapy prior to transition to Orenitram; a dose should be achieved that improves the symptoms of PAH while minimizing excessive pharmacologic effects of Remodulin. There is no maximum Remodulin dose during the study. If necessary, subjects can switch from IV to SC Remodulin, or SC to IV Remodulin, at the discretion of the Investigator.

Periodic contact between study site personnel and subjects should be conducted to monitor AEs between scheduled study visits (see Section 3.3.2.5). At the request of the Investigator, nursing support will assist subjects with initiation of SC or IV Remodulin, pump use, Remodulin dispensing, Remodulin titration, adverse event management, and transition assistance. Once the subject fully transitions off Remodulin, the study site will be the subject's primary/sole contact. Study site personnel will record the study drug dose at every study visit in the source documentation.

7.3.1 Week 2 (Day 15 [±3 Days])

Subjects will continue study drug dosing in the outpatient setting, as clinically appropriate. Subjects will return to the study site clinic for the following Investigator-reported assessments:

- Record of AEs
- WHO FC
- 6MWT (after 10 minutes rest [seated]), immediately followed by heart rate recovery (1 minute) and Borg dyspnea score. If the subject is receiving Orenitram, the 6MWT should occur within 2 to 6 hours of the most recent dose.
- Concomitant medications

- Vital signs (prior to or at least 30 minutes after the 6MWT, and after 5 minutes rest seated)
- Drug accountability (see Section 11.5)
- If the Transition Visit occurs at Week 2, please perform additional assessments listed in Section 7.3.4.

7.3.2 Week 4 (Day 29 [±5 Days])

Subjects will continue study drug dosing in the outpatient setting, as clinically appropriate. Subjects will return to the study site clinic for the following Investigator-reported assessments:

- Record of AEs
- WHO FC
- 6MWT (after 10 minutes rest [seated]), immediately followed by heart rate recovery (1 minute) and Borg dyspnea score. If the subject is receiving Orenitram, the 6MWT should occur within 2 to 6 hours of the most recent dose.
- Concomitant medications
- Vital signs (prior to or at least 30 minutes after the 6MWT, and after 5 minutes rest seated)
- Female subjects of childbearing potential will undergo a urine pregnancy test
- Drug accountability (see Section 11.5)
- If the Transition Visit occurs at Week 4, please perform additional assessments listed in Section 7.3.4.

Note: If the Transition Visit occurs at Week 2, the Week 4 visit can be substituted for the Post Transition Visit (ie, an extra visit is not necessary).

7.3.3 Week 8 (Day 57 [±5 Days])

Subjects will continue study drug dosing in the outpatient setting, as clinically appropriate. Subjects will return to the study site clinic for the following Investigator-reported assessments:

- Record of AEs
- WHO FC
- 6MWT (after 10 minutes rest [seated]), immediately followed by heart rate recovery (1 minute) and Borg dyspnea score. If the subject is receiving Orenitram, the 6MWT should occur within 2 to 6 hours of the most recent dose.

- Concomitant medications
- Vital signs (prior to or at least 30 minutes after the 6MWT, and after 5 minutes rest seated)
- Female subjects of childbearing potential will undergo a urine pregnancy test
- Drug accountability (see Section 11.5)
- If the Transition Visit occurs at Week 8, please perform additional assessments listed in Section 7.3.4.

7.3.4 Transition Visit (Week 2, 4, or 8)

Subjects may transition at Weeks 2, 4, or 8 if they have achieved a minimum Remodulin dose of 20 ng/kg/min and the Investigator deems the subject suitable for transition. Subjects will transition from Remodulin to Orenitram over the course of 1 to 21 days in an inpatient or outpatient setting using a cross-taper method (ie, decreases in Remodulin dose coincide with increases in Orenitram dose). Subjects will be instructed to take the appropriate number of Orenitram tablets based upon their Remodulin dose and the transition schedule chosen by their healthcare provider.

At the discretion of the Investigator, transition may also be reversed or stopped if necessary due to significant signs or symptoms of PAH or due to serious safety concerns. If the Investigator deems a subject unsuitable for transition to Orenitram due to significant signs and symptoms of PAH or any other serious safety concerns, the subject may remain on Remodulin for the duration of the study. However, the subject should be continually assessed to determine if they become stable enough for transition to Orenitram. All subjects still on Remodulin at Week 8 should transition to Orenitram at Week 8 regardless of their Remodulin dose unless the Investigator deems them unsuitable for transition to Orenitram due to significant signs and symptoms of PAH or any other serious safety concerns.

Transition will occur as follows:

- The dose of Remodulin can be reduced no more than 10 ng/kg/min per day for transitions in the outpatient setting. For inpatient transitions, there is no limit on the rate of Remodulin dose reduction.
- The target dose of Orenitram at the end of transition is dependent on the subject's weight and Remodulin dose. Up-titration of Orenitram should coincide with a reduction in the Remodulin dose. The target TDD of Orenitram at the end of

transition will be calculated based upon the following equivalence weight-based formula:

TDD [mg] = 0.0072 * Remodulin dose [ng/kg/min] * weight [kg].

- The Orenitram up-titration dose should be taken at approximately the same time the Remodulin dose is decreased.
- Examples of transition schedules for various subject body weights and Remodulin doses are listed in Appendix I.

The following subject-reported data will be completed by the subject at the Transition Visit prior to all other assessments and prior to initiation of Orenitram: emPHasis-10 questionnaire and TSQM.

The following assessments should be performed at the Transition Visit:

- PAH symptom score
- Record of AEs
- AE Bothersome Survey
- WHO FC
- Serum NT-proBNP (sample must be drawn prior to the 6MWT and Orenitram initiation)
- 6MWT (after 10 minutes rest [seated]), immediately followed by heart rate recovery (1 minute) and Borg dyspnea score (before initiating the transition to Orenitram)
- Concomitant medications
- Full physical examination
- ECHO
- Vital signs (prior to or at least 30 minutes after the 6MWT, and after 5 minutes rest seated)
- Female subjects of childbearing potential will undergo a urine pregnancy test
- Drug accountability (see Section 11.5)
- Clinical laboratory assessments
- Optional biomarker blood sample

Following transition, Orenitram dose titration may continue in the outpatient setting through Week 16 to reach the maximum tolerated dose by increasing the dose by 0.125 mg TID every 3 to 4 days as tolerated, with the goal of achieving a maximum tolerated dose by the end of

Week 16. A slower titration rate may be used if the subject experiences adverse effects. There is no maximum Orenitram dose during the study.

7.3.5 Post Transition Visit (7 to 14 days after Transition Visit)

Subjects will continue study drug dosing in the outpatient setting, as clinically appropriate. Subjects will return to the study site clinic for the following Investigator-reported assessments:

- Record of AEs
- WHO FC
- 6MWT (after 10 minutes rest [seated]), immediately followed by heart rate recovery (1 minute) and Borg dyspnea score. The 6MWT should occur within 2 to 6 hours of the most recent dose of Orenitram.
- Concomitant medications
- Vital signs (prior to or at least 30 minutes after the 6MWT, and after 5 minutes rest seated)
- Drug accountability (see Section 11.5)

Note: If the Transition Visit occurs at Week 2, the Week 4 visit can be substituted for the Post Transition Visit (ie, an extra visit is not necessary).

7.3.6 Week 12 (Day 85 [±5 Days])

Subjects will continue study drug dosing in the outpatient setting, as clinically appropriate. Subjects will return to the study site clinic for the following Investigator-reported assessments:

- · Record of AEs
- WHO FC
- 6MWT (after 10 minutes rest [seated]), immediately followed by heart rate recovery (1 minute) and Borg dyspnea score. If the subject is receiving Orenitram, the 6MWT should occur within 2 to 6 hours of the most recent dose.
- Concomitant medications
- Vital signs (prior to or at least 30 minutes after the 6MWT, and after 5 minutes rest seated)
- Female subjects of childbearing potential will undergo a urine pregnancy test
- Drug accountability (see Section 11.5)

7.3.7 Week 16/Early Study Withdrawal (Day 113 [±7 Days])

The following subject-reported data will be completed by the subject at the Week 16/Early Study Withdrawal Visit prior to all other assessments: emPHasis-10 questionnaire and TSQM.

The assessments of Week 16/Early Study Withdrawal Visit can occur over 5 days so that assessments can take place on separate days if needed. All assessments should be conducted prior to withdrawing from the study, prior to discontinuation of Orenitram or Remodulin, and as close as possible to the last dose taken by the subject.

Subjects will return to the study site clinic for the following Investigator-reported assessments:

- PAH symptom score
- · Record of AEs
- AE Bothersome Survey
- ECHO
- WHO FC
- Serum NT-proBNP (samples must be drawn prior to the 6MWT)
- 6MWT (after 10 minutes rest [seated]), immediately followed by heart rate recovery (1 minute) and Borg dyspnea score. If the subject is receiving Orenitram, the 6MWT should occur within 2 to 6 hours of the most recent dose.
- Clinical laboratory assessments
- Vital signs (prior to or at least 30 minutes after the 6MWT, and after 5 minutes rest seated)
- Concomitant medications
- Full physical examination
- Optional biomarker blood sample
- Female subjects of childbearing potential will undergo a urine pregnancy test
- Drug accountability (see Section 11.5)

Subjects who complete the Week 16 Visit will be transitioned off clinical study material to commercially available Orenitram or Remodulin, as clinically appropriate.

8 STUDY TERMINATION

8.1 CRITERIA FOR SUBJECT WITHDRAWAL

A subject may voluntarily withdraw or be withdrawn from the study and/or study drug by the Investigator at any time for reasons including, but not limited to, the following:

- The subject wishes to withdraw from further participation.
- A serious or life-threatening AE occurs or the Investigator considers that it is necessary to discontinue study drug to protect the safety of the subject.
- The subject deviated from the protocol.
- The subject's behavior is likely to undermine the validity of his/her results.

If a subject is discontinued from the study prematurely, the Investigator must provide an explanation in the eCRF (Investigator's Comment Log) and complete the End of Study Record for that subject. If study drug has been administered, the Investigator should make every effort to perform all scheduled evaluations prior to discharge. In the event that a subject discontinues study drug prematurely due to an AE, the subject will be followed until either the Investigator determines that the AE has resolved, it is no longer considered clinically significant, the subject is lost to further follow-up, or for 4 weeks if the AE extends beyond the final visit.

If a subject discontinues study drug prior to completing the Week 16 Visit assessments, the Investigator will record the reason for withdrawal (eg, type of AE, lack of response), the dosing titration schedule (date and dose of last titration, date and last dose taken before study drug discontinuation), and if transitioning to a different pulmonary hypertension therapy, the pulmonary hypertension drug to which the subject is transitioning.

8.2 CRITERIA FOR TERMINATING THE STUDY

The study may be stopped at any time if, in the opinion of the Investigator and/or Sponsor, continuation of the study represents a serious medical risk to the subjects. This may include, but is not limited to, the presence of serious, life-threatening, or fatal AEs or AEs that are unacceptable in nature, severity, or frequency. The Sponsor reserves the right to discontinue the study for any reason at any time.

8.3 CRITERIA FOR DISCONTINUING THE SITE

The study may also be terminated at a given center if:

- The Investigator elects to discontinue the study
- The Sponsor elects to discontinue the study at the study site
- United States FDA regulations or International Council for Harmonisation (ICH)
 Good Clinical Practice (GCP) guidelines are not observed
- The protocol is violated or critical violations are documented, or
- Changes in personnel or facilities adversely affect performance of the study

9 ADVERSE EVENT REPORTING

9.1 **DEFINITIONS**

9.1.1 Adverse Event

An AE is any untoward medical occurrence in a subject occurring to a subject during a clinical study whether or not it is related to the study drug. An AE may include an intercurrent illness, injury, or any other concomitant impairment of the subject's health, as well as abnormal laboratory findings if deemed to have clinical significance. Adverse events may also include worsening of an existing symptom or condition or post-treatment events that occur as a result of protocol-mandated procedures.

Events related to prostanoid therapy captured by the AE Bothersome Survey (Appendix E) should only be recorded as an AE and should only be captured as an SAE if the event is unusual with respect to intensity, frequency, or duration as compared with symptoms in the subject's medical history.

Events attributable to the progression of the disease under study (listed in Table 9-1) and events attributable to PAH symptomatology captured by PAH Symptom Score (Section 3.3.1.2) should be recorded as an AE or captured as an SAE if the event is unusual with respect to intensity, frequency, or duration as compared with symptoms in the subject's medical history, or if there is a reasonable possibility that the event was caused by the study drug.

Anorexia Palpitations

Abdominal pain Peripheral edema/generalized edema

Dizziness Presyncope

Dyspnea/dyspnea on exertion Pulmonary hypertension, exacerbation of

Exercise tolerance decreased Right heart failure/right ventricular failure

Syncope

Weight loss

Weight gain

Table 9-1 Adverse Events Attributable to the Progression of Disease

Note: Symptoms of right ventricular failure/right heart failure can include, but are not limited to, ascites, cyanosis, tachycardia, and other cardiac arrhythmias. The effects of pulmonary hypertpension and right ventricular failure/right heart failure can include cardiac arrest and death.

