3.3.2 Safety

3.3.2.1 Adverse Events and the AE Bothersome Survey

Adverse events will be captured from when the subject signs the informed consent form (ICF) until the subject completes the study or is withdrawn from the study. Adverse events should be followed until either resolution (or return to normal or Baseline values), until they are judged by the Investigator to no longer be clinically significant, or for at least 4 weeks if the AE extends beyond the final study visit (Week 16). All serious adverse events (SAEs) that occur during the study will be followed until resolution, death, or the subject is lost to follow-up, even if they are ongoing more than 4 weeks after completion of the final study visit.

The Investigator will administer the AE Bothersome Survey (Appendix E) at time points listed in Table 3-1 to collect information about prostanoid-related effects experienced by the subject. This questionnaire may be used to guide AE assessment and conversations about AEs that a subject is experiencing.

Events related to prostanoid therapy captured by the AE Bothersome Survey (Appendix E) should only be recorded as an AE and should only be captured as an SAE if the event is unusual with respect to intensity, frequency, or duration as compared with symptoms in the subject's medical history.

Events attributable to the progression of the disease under study (listed in Table 9-1) and events attributable to PAH symptomatology captured by PAH Symptom Score (Section

3.3.1.2) should only be recorded as an AE if the event is unusual with respect to intensity, frequency, or duration as compared with symptoms in the subject's medical history, or if there is a reasonable possibility that the event was caused by the study drug

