9.1.2 Serious Adverse Event

An SAE is an AE occurring at any dose that results in any of the following outcomes:

Death

Fatigue

Hypoxia

Lethargy

Loss of consciousness

- A life-threatening AE
- Inpatient hospitalization or prolongation of existing hospitalization
- A persistent or significant disability/incapacity
- A congenital anomaly/birth defect
- Results in a medically important event or reaction

In addition, important medical events that may not result in death, be life-threatening, or require hospitalization may be considered serious when, based upon appropriate medical judgment, they may jeopardize the subject and require medical/surgical intervention to prevent 1 of the outcomes listed above. Examples of such medical events include allergic bronchospasm requiring intensive treatment in an emergency room or at home, blood dyscrasias or convulsions that do not result in hospitalization, or the development of drug dependency or drug abuse.

Life-threatening means that the subject was, in the view of the Investigator, at immediate risk of death from the event as it occurred. It does not mean that the event, had it occurred in a more severe form, might have caused death.

For this study, SAE reporting responsibilities will be as per Section 9.3. All SAEs that occur during the study will be followed until resolution, death, or the subject is lost to follow-up, even if they are ongoing more than 30 days after completion of the final study visit (Week 16 Visit or Early Withdrawal Visit).

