9.3 REPORTING RESPONSIBILITIES OF THE INVESTIGATOR

All SAEs, regardless of expectedness or causality, must be reported in the ClinTrak EDC system within 24 hours of awareness. Follow-up SAE information should be reported to United Therapeutics GDS within 24 hours of the receipt of any new/updated information by entering it into the EDC system.

In the event the ClinTrak EDC system is unavailable, the SAE should be reported on the SAE Notification Form to United Therapeutics GDS by e-mail or fax

Fax-Americas/Japan

) in order to meet the 24-hour reporting deadline. The SAE must be recorded in the ClinTrak EDC system as soon as it becomes available. Any relevant medical records should be sent to United Therapeutics GDS by fax or email.

Serious AEs (which the study site was unaware of) that are reported directly to United Therapeutics GDS by the contract research organization or nursing support will be forwarded to the study site. Study site personnel shall record these events in the EDC.

The Investigator must also promptly notify their Institutional Review Board (IRB) or Independent Ethics Committee (IEC) of the SAE, including any follow-up information, in accordance with applicable national regulations and guidelines set forth by the IRB/IEC.

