A serious adverse event (SAE) is one that represents an actual or potential significant hazard. This includes, but is not limited to, an event that is fatal, life-threatening, permanently or severely disabling, requires or prolongs inpatient hospitalization*, is a congenital abnormality (offspring of subject), or is medically significant (important medical events that may not result in death, be life-threatening, or require hospitalization can be considered an SAE when, based upon appropriate medical judgment, they could jeopardize the subject and could require medical or surgical intervention to prevent one of the outcomes listed in the definition).

*Hospitalizations that would not be considered SAEs include those for:

- Routine treatment or monitoring of the study indication not associated with any deterioration in condition (eg, hospitalization for a routine right heart catheterization).
- Treatment which was elective or preplanned, for a pre-existing condition not associated with any deterioration in condition (eg, preplanned operation which does not lead to further complications, etc).
- Treatment of any emergency, in an outpatient setting for an event not fulfilling any of the definitions of seriousness as listed above and not resulting in hospital admission.

Causality

An estimate of causality between a specified adverse event and the study drug is made by the Investigator. Several factors should be considered when determining causality. These factors include temporal relationship and response to withdrawal or reintroduction of the study drug.

Definitions of the causality categories are as follows:

- NOT RELATED There is not a temporal relationship to study drug administration (too early, or late, or study drug not taken), or there is a reasonable causal relationship between another drug, or concurrent disease and the SAE, or any of the following:
 - An event that precedes the first administration of study drug
 - An event for which the cause is clearly related to an external event
 - Temporal relationship to study drug is atypical

- Is readily explained by an intercurrent illness AND has an expected level of severity, duration and resolution
 - An alternative explanation (concomitant drug, intercurrent illness) is likely

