Appendix E. AE Bothersome Survey

Investigators will ask subjects about the prostanoid-related effects they experienced using the AE Bothersome Survey. For this study, adverse events of interest include headache, diarrhea, nausea, flushing, jaw pain, extremity pain, and vomiting. Scores will be captured at the time points listed in Table 3-1. The Investigator will begin with Question 1, asking the subject about the AEs listed in the left-most column, and proceed to Question 2 and Question 3 for any AEs experienced by the subject. This questionnaire may be used to guide AE assessment and conversations about AEs that a subject is experiencing. Events captured by the AE Bothersome Survey should only be recorded as an AE and should only be captured as an SAE if the event is unusual with respect to intensity, frequency, or duration as compared with symptoms in the subject's medical history (see section 9.1).

AE Bothersome Survey													
Question 1			Question 2				Question 3						
"Have you experie health problem or side effect in the particle yes of proceed to Question Question 3.)	medicati ast week or no . If	ion ?" yes,	"For this health problem or medication side effect that you experienced, how bothersome has it been for you during the last week using the following scale?" 1 – bothers me a lot 2 – bothers me some 3 – bothers me a little 4 – not at all bothersome			that you experienced, how bothersome been for you during the last week using lowing scale?" there me a lot there me some there me a little "For this health problem or medication side effect that you experienced, ho many days in the week did you experience it?"				e ow ne p	ast		
			(Please circle of Question 3.)	ne numb	er and pi	roceed to	-	eas					7.)
Headache	Yes	No	1	2	3	4	1	2	3	4	5	6	7
Diarrhea	Yes	No	1	2	3	4	1	2	3	4	5	6	7
Nausea	Yes	No	1	2	3	4	1	2	3	4	5	6	7
Flushing	Yes	No	1	2	3	4	1	2	3	4	5	6	7
Jaw pain	Yes	No	1	2	3	4	1	2	3	4	5	6	7
Extremity pain	Yes	No	1	2	3	4	1	2	3	4	5	6	7
Vomiting	Yes	No	1	2	3	4	1	2	3	4	5	6	7

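### The rule that prostanoid events count as SAEs only if unusual for the subject contradicts the protocol's own SAE definition and reporting rule, so a serious event could lose SAE status

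*Protocol*

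**What the plan says.** **The special rule.** Protocol 9.1.1 says that events related to prostanoid therapy which the AE Bothersome Survey picks up "should only be recorded as an AE and should only be captured as an SAE if the event is unusual". Unusual is judged on intensity, frequency or duration against symptoms in the subject's medical history. Section 3.3.2.1 has the same sentence, and Appendix E repeats it: "Events captured by the AE Bothersome Survey should only be recorded as an AE and should only be captured as an SAE" under the same condition. The survey covers headache, diarrhea, nausea, flushing, jaw pain, extremity pain and vomiting.

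**The general rules.** Protocol 9.1.2 defines seriousness by outcome: "An SAE is an AE occurring at any dose that results in any of the following outcomes". One listed outcome is "Inpatient hospitalization or prolongation of existing hospitalization". Section 9.3 adds: "All SAEs, regardless of expectedness or causality, must be reported in the ClinTrak EDC system within 24 hours of awareness". Appendix C asks that intensity be judged separately from seriousness. It also has a list that opens "Hospitalizations that would not be considered SAEs include those for", with three kinds of admission or emergency treatment, none of them for prostanoid effects.

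**The analysis.** SAP 3.7.1 tabulates SAEs and TESAEs as recorded. It summarizes the seven prostanoid AEs by count and maximum severity in each treatment phase, with no breakdown by seriousness.

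**The concern.** The two sets of rules give different answers for the same event. Under 9.1.2 an admission to hospital makes an event serious. Under 9.1.1 the same admission for a survey-captured prostanoid effect is not an SAE if the investigator finds the effect in line with the subject's history.

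These are the expected harms of the regimen, and tolerability is part of the secondary objective. Because SAP 3.7.2 says that vital signs and laboratory tests will be neither listed nor summarized, the AE tables carry most of the safety evidence. The interim in SAP 4.1 compares the safety profile with historical transition data. An SAE count that passed through a history filter may not be comparable with counts that did not.

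**Working it through.** The plan gives no figure to reproduce, because the study is descriptive and states no expected rate of serious prostanoid events. The check is a comparison of texts, followed by simple arithmetic for scale.

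**Step 1. Set the rules side by side.**

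| Place in the protocol | What decides SAE status or reporting | Is history relevant? |
|---|---|---|
| 3.3.2.1, 9.1.1, Appendix E (prostanoid events) | Unusual intensity, frequency or duration | Yes, it is the test |
| 9.1.2 and Appendix C (all AEs) | Outcome, such as death, threat to life or hospitalization | No |
| 9.3 (all SAEs) | Being an SAE; expectedness and causality are set aside | No |
| Appendix C (intensity) | Intensity is kept apart from seriousness | No |

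The first row conflicts with each of the others. Comparing an event with the subject's history is close to an expectedness filter, which 9.3 excludes. Using intensity to settle SAE status is what Appendix C tells the investigator not to do. The rule appears in three places, so it is not a one-line slip.

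**Step 2. Compare with the parallel rule.** Sections 3.3.2.1 and 9.1.1 also apply a history test to disease-progression events, but both add an alternative: a reasonable possibility that the study drug caused the event. The prostanoid sentence has no such clause, although it concerns events attributed to prostanoid therapy. The disease-progression sentence also differs between its two places. Section 3.3.2.1 makes AE recording conditional and does not mention SAEs; 9.1.1 covers both AE recording and SAE capture.

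**Step 3. Follow one event.** Take a subject admitted for vomiting that the investigator judges not unusual in intensity, frequency or duration.
- Under 9.1.2 and 9.3 it is an SAE, due for report within 24 hours and followed until resolution, death or loss to follow-up.
- Under 9.1.1 it is an AE only. The 24-hour report does not apply, and follow-up may end once the investigator judges the event no longer clinically significant.
- The separate reporting route for nonserious AEs in 9.2 covers only events outside the seven prostanoid AEs, so it does not catch this event either.
- In the SAP tables it appears among TEAEs and prostanoid AEs, but not among SAEs or TESAEs.

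**Step 4. Scale.** For one subject whose only serious event is not captured as an SAE, the percentage of subjects with an SAE falls by 100 × 1/n:
- n = 30 (protocol 10.2): 100/30 = 3.3 points
- n = 35 (SAP 2.2.3): 100/35 = 2.9 points
- n = 10 (interim, SAP 4.1): 100/10 = 10 points

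The first two lines assume that the Safety Population is about as large as the evaluable number. If more subjects are dosed, the shift is somewhat smaller.

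**The case against.** Much of the case for leaving the text alone is fair, and it limits the point.

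- **Do the events vanish from the data?** A reader might infer that a prostanoid event is recorded as an AE only if unusual. The wording is loose enough to allow that, but the documents point the other way. The sentence has two separate clauses, and the condition sits naturally with the second. Section 9.2 expects subjects to report prostanoid AEs, 3.3.1.9 links concomitant medications to them, and SAP 3.7.1 counts them. On the natural reading they remain AEs.
- **Does the rule cover all prostanoid events?** Literally it covers those captured by the survey, which asks about the past week at Baseline, the Transition Visit and Week 16/Early Study Withdrawal. Other prostanoid events fall under 9.1.2 without the filter. This narrows the reach, but it makes SAE status depend on whether an event fell in a survey week.
- **Does any history of migraine or vomiting remove SAE status?** No. The event fails the test only if intensity, frequency and duration are all judged not unusual, and an admission will often differ on at least one. The exclusion of prostacyclin-class therapy within 28 days of Baseline also makes recent prostanoid symptoms less likely in the history. It does not remove histories of headache, gastrointestinal illness or pain from other causes.
- **Is seriousness recorded anyway?** Section 9.2 lists it among the eCRF items. But 9.1.1 tells the investigator when SAE status may be given, so the field does not settle the conflict.
- **Can a percentage of missed SAEs be stated?** No. The documents give no expected number, and protocol 1.2.3 describes the most frequent AEs with Remodulin as generally not serious.

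None of this says which rule governs when they disagree, so the contradiction stands.

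**Conclusion.** The protocol contradicts itself on when a survey-captured prostanoid event is an SAE. An investigator who follows 9.1.1 as written can withhold SAE status, the 24-hour report and SAE follow-up from an event that 9.1.2 makes serious. The event would normally still be counted as an AE. It is a possible misclassification, not a demonstrated loss of safety data.

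The number of events affected is unknown and may be zero. The shifts per subject given above apply only if such an event occurs, is judged not unusual, and is that subject's only serious event. The point deserves correction because the wording is plain, occurs three times and touches the harms of most interest, not because a large effect can be shown.

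**What to change.** 1. In protocol 3.3.2.1, 9.1.1 and Appendix E, make the seriousness of prostanoid events depend on 9.1.2 alone. Either delete the condition on unusualness or state that 9.1.2 and 9.3 take precedence over it.
2. State in the same places that all prostanoid events are recorded as AEs, which removes the second reading.
3. Give the disease-progression sentence one wording in 3.3.2.1 and 9.1.1, and reconcile it with 9.1.2.
4. In SAP 3.7.1, state that prostanoid AEs meeting a seriousness criterion enter the SAE and TESAE tables.

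The cost is a protocol wording amendment with the approvals required by section 13.1, a reminder to the approximately 13 centers, one sentence in the SAP and possibly a few more SAE forms. No visit, assessment or treatment changes.
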